#### 3.3 ASSESSMENTS

Assessments for patients with high grade gliomas are as follows:

- Background information (gender, age, ethnicity etc)
- Full medical history (personal health history (any previously known health problems) and family health history (details about health problems that blood relatives have had during their lifetimes)
- Diagnosis
- Medications that you are currently on
- Physical examination guided by clinical consultation
- Performance status
- Any other know health conditions (ACE 27 Questionnaire)
- Recent imaging and blood tests performed for routine clinical practice
- A brief assessment of your memory and concentration which normally takes 5-10 minute (MoCA)

Assessments for caregivers are as follows

- Background information (gender, age, ethnicity etc)
- Performance status
- Any other know health conditions (ACE 27 Questionnaire)

IRAS number 266261

#### 3.4 QUESTIONNAIRES

Patients will be asked to complete the following questionnaires at certain study time points:

- PGI is a three-step process: Patients lists five areas most affected by illness and an initial box asks, "all other areas of your life affected by your cancer and treatment." Patient rates each of the 6 areas on a scale 0 (worst imaginable) to 6 (very best imaginable); Patient distributes 10 points between the 6 areas with the most points going to the more important areas
- EORTC QLQ30 covers five functioning scales (physical, social, role, cognitive, and emotional functioning), eight symptom scales (fatigue, nausea/vomiting, pain, dyspnea, sleep disturbances, appetite loss, constipation, and diarrhea), financial impact, and overall quality of life, and the scores are linearly converted to range between 0 to 100. High scores in the functioning scale and global QoL indicate better function whilst a higher score in the symptom scale indicate higher symptom burden.
- EORTC QLQ-BN20 questionnaire covers a further 11 scales to assess neurological deficits (visual disorder, motor dysfunction, communication deficit), future uncertainty, and disease- and treatment-related symptoms. Similar to the EORTC QLQ30 the raw scores are converted to a 0-100 scale and a higher score for this questionnaire represents a poorer QoL.
- EQ-5D-5L is a short, quick and cognitively undemanding assessment consisting of 5 questions and a Visual Analog Scale. It has been used in a wide range of health conditions and treatments and therefore makes it an ideal tool for comparative assessment. Furthermore, the EQ-5D-5L can then be adapted to a single index value.
- ACE 27 Questionnaire, taken at enrolment only by a member of the research study team. To assess background health status of patient.

Caregivers will be asked to complete the following questionnaires at certain study time points

- CaGI which will be based on the same concept as the PGI three-step process: Caregiver lists five areas most affected by illness and an initial box asks, "all other areas of your life affected by your loved one's cancer and treatment." Caregiver rates each of the 6 areas on a scale 0 (worst imaginable) to 6 (very best imaginable); Caregiver distributes 10 points between the 6 areas with the most points going to the more important areas
- CareGiver Oncology Quality of Life (CarGOQOL) questionnaire. A validated tool for use with partners, parents and children of oncology patients contains 29 items covering 10 domains (psychological well-being, burden, relationship with healthcare, administration and finances, coping, physical well-being, self-esteem, leisure time, social support and private life)
- EQ-5D-5L is a short, quick and cognitively undemanding assessment consisting of 5 questions and a Visual Analog Scale. It has been used in a wide range of health conditions and treatments and therefore makes it an ideal tool for comparative

## Imperial College

assessment. Furthermore the EQ-5D-5L can then be adapted to a single index value.

ACE 27 Questionnaire, taken at enrolment only by a member of the research study team. To assess background health status of caregivers.

#### 3.5 RECRUITMENT PROCESS

Participants will be recruited from three tertiary care centres (Imperial College Healthcare NHS Trust, Barts Health NHS Trust and Guys & St Thomas NHS Foundation Trust). Potential participants will include any patient that is referred to the Brain Tumour MDT and/or neuro-oncology clinic with a suspected new, or recurrent, high grade brain tumour and plan is for:

- neurosurgical biopsy or resection,
- start a course of radical radiotherapy (≥45 Gy)
- course of chemoradiotherapy
- stereotactic radiotherapy
- or for re-treat for relapsed disease.

As clinically indicated, patients will come to their clinic appointment, normally with a caregiver, to discuss treatment options. At this point, the treating doctor/ [name]/ member of the study team will provide patient and caregiver with a written patient information sheet (PIS) to read. Both the caregiver and patient should be given sufficient time to consider whether or not they would like to participate in the study. If the patient and caregiver feel that they have a full understanding of the research and what it entails and have had the opportunity to ask any questions they may have, a member of the study team will consent them onto the study and complete the baseline Case Report Form (CRF).

Participants will be divided into three cohorts for eligibility/ recruitment into the study:

- 1. Patient and caregiver both consent for study
- 2. Patient consents for study and the caregiver does not consent to take part in study
- 3. Patient does not consent to being part of study but gives consent for research team to have access to medical records. Caregiver consents to being enrolled into study.

Participants will then take part in an observational, longitudinal study of HRQoL from diagnosis to six months. The assessment process will be as follows:

- 1. Screening of patients from Brain MDT and Neuro-Oncology clinics
- 2. Patient comes to clinic (as clinically indicated) with caregiver

- 3. Caregivers will be approached to take part in the study if they attend one of the initial outpatient appointments with the patient participant and will be given a separate participant information sheet (PIS) and consent form to sign.
- 4. Patient/ caregiver given PIS to read. If patient/ caregiver feels that they have a full understanding of the research and what it entails, they will be given the consent form to sign to provide informed consent
- 5. Patient/ caregiver enrolment into the study
- 6. Explanation of how PGI/ CaGI will be completed at each time visit
- 7. Baseline assessments to be completed (see trial schema in assessment and follow up)
- 8. At each visit, patient/ caregiver completes the PGI/CaGI first followed by standard HRQoL measures
- 9. Patients and caregivers will be given the opportunity to complete assessments online where study sites (i.e. Hospital Trusts) are already using secure online portals for patient care as these are an acceptable method of gathering patient data. These portals will only be used if they already have approval from the trust and are used as part of routine clinical care. We are keen to include the use of such methods, as otherwise we run the risk of forcing a backward step (i.e. taking sites that use a portal and then forcing them back to paper-based data collection).
- 10. Assessments will be done at baseline, 6 weeks, 3,4 and 6 months (see trial schema in assessment and follow up)- we will assess at an individual participant level the best way to complete assessments e.g. on paper or using online mechanisms
- 11. With ongoing consent, patients and caregivers will be followed from enrolment for 6 months or to discontinuation of treatment or death. If a participating patient is discontinued from active treatment, they and their caregiver will be approached to continue with the research assessment timetable. In discussion, these future assessments could be completed remotely (via telephone or video call) to prevent coming to the hospital.

#### 3.6 CONSENT

If a person is happy to participate in the study, one of the study team will obtain informed consent and we will complete baseline assessments. We will make people aware that the study is voluntary and that they do not have to take part. The decision to take part will not affect their care or treatment, including their relations with the direct care team. Given the low risk nature of this study, and in line with our other observational studies, we will allow participants to give consent and enrol on the same day. However, we are also happy for people to be given the PIS and enrol later. Potential participants will be given the time to consider fully the implications of taking part in research and this may vary between people. Once people have had enough time to process and ask questions, should they have any, signed informed consent can be taken. The right of people to refuse to participate without giving reasons shall be respected.

If a patient does not want to take part in the study, and a Caregiver does, informed consent will be taken from the Caregiver to participate, and consent will be taken from the patient to gain access to the patient's medical record.

All participants are free to withdraw at any time from the protocol treatment without giving reasons and without prejudicing further treatment. If a patient loses their capacity to consent whilst taking part in the study, we will retain any existing data collected, but will not collect any further data and the patient will be withdrawn from the study.

#### 3.7 DATA COLLECTION

For this study we will utilise a similar method as Hogan et al 2013 for undertaking the process of PGI and CaGI. We will provide a trigger list of sample areas/ concerns that are commonly raised in the literature on HRQoL in brain tumour patients and caregivers. Participants will be allowed to make use of one or more items from this list or generate their own.

As part of the study assessments, we will undertake audio recordings of the assessment sessions. These will be used to provide an unbiased record of the research process and may be used for further research in the future.

#### 3.8 STUDY OUTCOME MEASURES

Primary Outcome measures

- 1. Feasibility and acceptability of novel, personalised measures of HRQoL in patients with brain tumours and their caregivers, which will be assessed using completion rates.
- 2. Similarities and differences in ratings of HRQoL between novel, personalised and standard measures in patients with brain tumours and their caregivers, over a period of 6 months
- 3. Correlation, variation and stability between PGI/ CaGI and standard measures over time; in relation to treatment, disease progression and cognitive function

#### Secondary Outcome measures

- 1. Patterns of response to PGI/ CaGI and changes in impact on quality of life for both caregivers and patients with brain tumours
- 2. Correlation and divergence over time between QoL scores expressed by patients and caregivers
- 3. Patient, caregiver and professional views on the comparative benefits and drawbacks of standard approaches and PGI/ CaGI

## Imperial College

London

### 4. PARTICIPANT ENTRY

#### 4.1 INCLUSION CRITERIA

#### Inclusion Criteria -Patient

- 1. Newly diagnosed, or recurrent, high-grade primary brain tumour. We define a high-grade tumour as any grade 3 or 4 primary brain tumour (including meningioma).
- Newly diagnosed patients intending to undergo neurosurgical biopsy or resection, or to start a course of radical (≥45Gy) radiotherapy or a course of chemoradiotherapy or stereotactic radiotherapy.
- **3.** Recurrent brain tumours patients undergoing further treatment including surgery, chemotherapy or re-irradiation.
- 4. Performance status 0, 1, or 2
- 5. Able to provide written informed consent.
- 6. Intention to attend at least 5 clinic visits over a six-month period to the study site
- 7. Age 18 years and above
- 8. Willing to undertake study-specific measures

#### Inclusion Criteria -Caregiver

- 1. Main caregiver of patient with newly diagnosed or recurrent high-grade primary brain tumour.
- 2. Caregiver of patient receiving treatment (surgery and/or radiotherapy/ chemotherapy) expected to last  $\geq$  3 weeks in total
- 3. Aged 18 and above
- 4. Intention to attend at least 5 clinic visits over a six-month period to the study site.
- 5. Willing to undertake study-specific measures
- 6. Able to provide written informed consent

#### 4.2 EXCLUSION CRITERIA

Exclusion Criteria -Patient

- 1. Diagnosed with a low-grade brain tumour (including grade 1 and 2 meningiomas)
- 2. Poor performance status (PS 3,4) or rapidly deteriorating fitness and for best supportive care and/or symptom control only.
- 3. Diagnosed with a high-grade brain tumour but not planned for any intervention.
- 4. Language barriers
- Poor cognition status based on clinical assessment/ Montreal Cognitive Assessment (MoCA)/ MDT
- 6. Refusal to participate

#### **Exclusion Criteria -Caregiver**

- 1. Severe cognitive problems based on the doctor's opinion
- 2. Language barrier

3. Ongoing active treatment for own medical condition expected to significantly limit attendance for study assessments (missing 2 or more clinic visits). To be assessed by attending clinical or research team.

#### 4.3 WITHDRAWAL CRITERIA

The right of the participant to refuse to participate without giving reasons shall be respected. After the participant has entered the study the clinician will remain free to give alternative treatment to that specified in the protocol at any stage if he/she feels it is in the participant's best interest, but the reasons for doing so shall be recorded. In these cases, the participants remain within the study for the purposes of follow-up and data analysis. All participants are free to withdraw at any time from the protocol treatment without giving reasons and without prejudicing further treatment. If a patient loses their capacity to consent whilst taking part in the study, we will retain any existing data collected, but will not collect any further data and the patient will be withdrawn from the study.

#### 5. ASSESSMENT AND FOLLOW-UP

Patients will undergo standard follow up procedures (both clinical and imaging assessment) as part of their routine clinical care (monthly if on chemo-radiotherapy and 3-6 monthly during the follow up), and for this study will be followed from enrolment until 6 months. We intend to complete both patient and caregiver assessments at the same clinic visits. At all visits, the PGI/CaGI will be completed prior to any other assessment (EORTC QLQ30, BN20, CarGOQoL and EQ-5D-5L). At each visit the PGI/CaGI is completed anew, this will allow assessment of change in domains highlighted and the weighting ascribed to them.

To assess their previous medical history and concurrent medical conditions, the attending medical professional or researcher will complete the Adult Co-Morbidity Evaluation 27 with the caregiver at enrolment.

Patients and caregivers will be free to withdraw from the study at any time.

For validation purposes, on three visits patients and caregivers will be required to complete an additional assessment, EQ-5D-5L. This is a short, quick and cognitively undemanding assessment consisting of 5 questions and a Visual Analogue Scale. It has been used in a wide range of health conditions and treatments and therefore makes it an ideal tool for comparative assessment. Furthermore, the EQ-5D-5L can then be adapted to a single index value.

The end of the study is at the end of 6 months of follow up, discontinuation of treatment or death

		Enrolment/ Baseline	Week 2	Week 6	Month 3	Month 4	Month 6	Unexpected Visit
Patient	Demographic information	+						
	Medical history	+						
	Adult Co-Morbidity Evaluation 27	+						
	Diagnosis	+						
	MOCA assessment	+			+		+	
	EQ-5D-5L	+			+		+	
	Clinical information, Medication and imaging results	+	+	+	+	+	+	+
	ECOG PS	+	+	+	+	+	+	+
	Recent hospitalization	+	+	+	+	+	+	+
	PGI	+	+	+	+	+	+	+
	EORTC QLQ C30 & BN20	+	+	+	+	+	+	+
		Enrolment/ Baseline	Week 2	Week 6	Month 3	Month 4	Month 6	Unexpected Visit
Caregiver	Demographic information	+						
	Adult Co-Morbidity Evaluation 27	+						
	EQ-5D-5L	+			+		+	
	ECOG PS	+	+	+	+	+	+	+
	CaGI	+	+	+	+	+	+	+
	CarGOQoL	+	+	+	+	+	+	+

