#### 3. STUDY DESIGN

CaPaBLE is a prospective, observational, phase 2 non-randomised pragmatic cohort study of patients and caregivers, from diagnosis to six months.

All baseline assessments will be carried out at the local site as these will normally be done at the time of consent. Once consent has been taken in person, the option of video or telephone consultations will be considered on a patient/ caregiver basis by the treating clinical team. This is an already established service provided by the Neuro-oncology team at Imperial NHS Trust for those that are unable to attend the appointment in person.

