### 8. STATISTICS AND DATA ANALYSIS

The CI, [name], and Co-investigator, [name], will deal with the day to day management of the study and will ensure data completion and will help collate and check the data.

We will apply for the study to be NCRN-badged therefore if successful the local NCRN research nurses will be able to provide recruitment support. At Imperial College Health Care Trust, data will be collected in clinic on iPads, on Care Information Exchange (CIE – secure online platform currently available at ICHT) or on paper by the dedicated study team and stored directly onto ICHT Trust computers. At the other centres data will be collected in clinic using iPads/paper by the site-specific study team and stored on local secure NHS computers. At the end of each month data collected will be transferred to the main ICHT computer in a pseudonymised format for analysis.

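### Weeks 2 and 6 (and month 4 on 3–6 monthly review) do not fall on routine clinic visits, so the single completion rate may mix delivery of the forms with their acceptability

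*Protocol*

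**What the plan says.** Section 5 gives the routine clinic frequency as "monthly if on chemo-radiotherapy and 3-6 monthly during the follow up" and says of the study forms: "We intend to complete both patient and caregiver assessments at the same clinic visits". The table in that section schedules the PGI with QLQ-C30/BN20, and the CaGI with CarGOQoL, at baseline and then at "Week 2 Week 6 Month 3 Month 4 Month 6", plus any unexpected visit. Section 3.5 item 10 gives a shorter list, without week 2: "Assessments will be done at baseline, 6 weeks, 3,4 and 6 months".

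Other routes to the form are described in three places:

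- Section 3 allows video or telephone consultation after consent, decided case by case by the treating team. It presents this as an existing service at the lead trust "for those that are unable to attend the appointment in person".
- Section 3.5 items 9 and 10 allow online completion, chosen per participant, but only through portals that a trust has already approved and uses in routine care.
- Section 3.5 item 11 offers telephone or video assessment once active treatment has stopped.

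Section 8 names an online platform, iPads and paper at the lead trust. For the remaining two centres it says: "At the other centres data will be collected in clinic using iPads/paper by the site-specific study team".

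Section 4.1 requires of patients, and in the same terms of caregivers: "Intention to attend at least 5 clinic visits over a six-month period to the study site". The first primary outcome in section 3.8 is feasibility and acceptability, "which will be assessed using completion rates".

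**The concern.** Some due dates have no routine appointment attached, and no section says how the form is then obtained at every centre. A form can be absent because the participant could not or would not complete it, or because nobody was in contact to offer it. A single completion rate does not distinguish these, although section 8.1 makes feasibility and acceptability the main aim of the study.

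The gaps are unlikely to be evenly spread. A patient on 3–6 monthly review has fewer routine visits near the due dates than one reviewed monthly, and the described capture routes differ between the lead trust and the other two centres. The third primary outcome relates scores to treatment, and section 8.3 examines centre as a variable. Missing forms linked to either would complicate those comparisons. Caregiver forms are intended for the patient's visits, so they are exposed to the same calendar.

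**Working it through.** The protocol states no expected completion rate, so there is no figure of its own to reproduce. The confidence intervals for correlations in section 8.1 play no part in this point.

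**Inputs.** Due times come from the section 5 table: 0, 2 and 6 weeks, then 3, 4 and 6 months. Review intervals come from section 5: 1, 3 or 6 months. Assumptions of this check: visits run from enrolment at a constant interval; 1 month = 365.25/12/7 = 4.35 weeks; no remote or extra contact takes place; the window is ±1 or ±2 weeks, because the protocol states none.

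**Step 1: distance in weeks from each due time to the nearest routine visit, |due time − visit time|.**

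| Review | Week 2 | Week 6 | Month 3 | Month 4 | Month 6 | Visits in 6 months, with baseline |
|---|---|---|---|---|---|---|
| Monthly | 2.0 | 1.7 | 0 | 0 | 0 | 7 |
| 3-monthly | 2.0 | 6.0 | 0 | 4.3 | 0 | 3 |
| 6-monthly | 2.0 | 6.0 | 13.0 | 8.7 | 0 | 2 |

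For example, week 6 on monthly review: 6 − 4.35 = 1.65. For week 2 the nearest visit is baseline itself, which already hosts its own form; the next monthly visit is 4.35 − 2 = 2.35 weeks later.

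**Step 2: ceiling = (baseline + due times within the window of a later visit) / number due.**

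| Review | Six times, ±1 week | Six times, ±2 weeks | Five times (section 3.5), ±1 week | Five times, ±2 weeks |
|---|---|---|---|---|
| Monthly | 4/6 = 67% | 5/6 = 83% | 4/5 = 80% | 5/5 = 100% |
| 3-monthly | 3/6 = 50% | 3/6 = 50% | 3/5 = 60% | 3/5 = 60% |
| 6-monthly | 2/6 = 33% | 2/6 = 33% | 2/5 = 40% | 2/5 = 40% |

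**Step 3: how firm the ceilings are.** If monthly is read as every 4 weeks, the six-time ceiling is 1/6 (17%) at ±1 week and 6/6 (100%) at ±2 weeks. The monthly ceiling therefore depends almost entirely on a window that the protocol leaves open. The 3- and 6-monthly ceilings do not change between the two windows, but they apply a follow-up interval from the day of enrolment, which is a worst case.

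**Step 4: do other provisions cover the off-calendar dates?** Routine review supplies 3 visits (3-monthly) or 2 visits (6-monthly) against the 5 that participants must intend to attend. The criterion states an intention; no section schedules research visits to make up the difference. The section 3 route presupposes an appointment that cannot be attended. The portal route depends on what each trust already runs. Item 11 of section 3.5 applies after treatment stops. Each helps in some cases, but none is stated as the procedure when a due date has no appointment.

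**The case against.** The strongest reply is that the protocol does not tie data collection to routine visits alone. Participants must intend to make at least 5 visits, which equals the number of times listed in section 3.5, so those meeting the criterion plan to attend more often than a 3- or 6-monthly calendar provides. Completion by paper or online is chosen for each person and is not tied to an appointment. Section 8 does not say that the other centres collect data only in clinic. Patients enter around treatment or re-treatment, when review may be more frequent, and the 3–6 monthly interval belongs to later follow-up. Deliverability is also a proper part of feasibility in a pragmatic study aimed at routine use. The standard questionnaires QLQ-C30/BN20 and CarGOQoL share the PGI/CaGI time points, so a missed contact affects both alike. Finally, the denominator may sit in a SAP that is not shown.

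Much of this stands. A reader might infer that the completion rate will measure the clinic calendar instead of feasibility, or that month 4 will be missed for many participants. The documents support neither: the remote and online routes are real, and the mix of treatment pathways is not given. The within-visit comparison of PGI/CaGI with those standard questionnaires is largely protected.

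What the reply does not meet is the absence of a stated procedure for off-calendar dates at every centre and for caregivers. Nor can a SAP recover whether a form was offered if the CRF never recorded it.

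**Conclusion.** The timing mismatch is in the protocol's own text. Weeks 2 and 6 match neither review pattern, and month 4 does not match 3–6 monthly review. Because one completion rate serves both feasibility and acceptability, it may be confounded by treatment pathway and centre.

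How far cannot be calculated. That would need the pathway mix, the visit windows, and the actual use of remote, portal and extra contacts, none of which the protocol gives. The 67%, 50% and 33% figures are ceilings for the case of routine visits only, a window of about one week and a constant interval from enrolment. They are not predictions of completion.

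This does not invalidate the design. It is a worthwhile and cheap improvement to a primary outcome, and it has to be made before data collection, since the information cannot be reconstructed later.

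**What to change.** 1. On the CRF, record for every due assessment whether contact occurred, whether the form was offered, and the mode of completion. Report two rates per instrument and time point, by centre: offered/due (delivery) and completed/offered (acceptability).
2. In sections 3, 5 and 8, state a window around each due date. When no clinic visit falls within it, extend the existing remote option (telephone, post, or a portal where approved) to all three centres, and to caregivers as well as patients.
3. Reconcile week 2, which is in the section 5 table but absent from section 3.5 item 10, so that the number of due assessments (six or five) is fixed.

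The cost is protocol and CRF wording and some calls by the existing study team. The small downside is a greater mix of completion modes, which item 1 records. Routine clinical follow-up is unchanged.

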	chemotherapy) expected to last >= 3 weeks in total				
	3.	Aged 18 and above			
	4.	Intention to attend at least 5 clinic visits over a six-month period to the study site.			
	5.	Willing to undertake study-specific measures			
	6.	Able to provide written informed consent			
DURATION	Study will be c	ppen for 2 years; Participants will be on study for 6 months			

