#### 2.2 OBJECTIVES

- 1. To explore the feasibility and acceptability of using PGI/ CaGI to assess HRQoL over time in patients with high-grade glioma (HGG) and their caregivers
- 2. To assess how changes in HRQoL as measured through standard approaches and personalised subsets + PGI/ CaGI relate to one another
- 3. To assess the impact of high grade, malignant primary brain tumours on quality of life in newly diagnosed patients and track changes in reported QoL throughout treatment and disease progression
- 4. To assess the impact on quality of life of being a caregiver for a patient with newly diagnosed, high grade, malignant primary brain tumours and track changes in reported caregiver QoL throughout treatment and disease progression
- 5. To identify differences and relationships between QoL scores expressed by patients and caregivers over time
- 6. To assess patient, caregiver and professional views on the comparative benefits and drawbacks of standard approaches and PGI/ CaGI

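### The protocol's rules for ending questionnaire follow-up conflict: two sentences stop it at an undefined discontinuation of treatment, while others run it to six months

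*Protocol*

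**What the plan says.** Two sentences make discontinuation of treatment an end of follow-up. The end-of-study sentence in section 5, directly above the visit schedule, reads: "The end of the study is at the end of 6 months of follow up, discontinuation of treatment or death". Section 3.5 item 11 opens with the statement that "patients and caregivers will be followed from enrolment for 6 months or to discontinuation of treatment or death".

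Three other places run to six months:
- Study Summary, Duration: "Participants will be on study for 6 months".
- Section 5, first paragraph: patients "for this study will be followed from enrolment until 6 months".
- Section 3.5 item 11, after its opening sentence: when a patient is discontinued from active treatment, "they and their caregiver will be approached to continue with the research assessment timetable", and "these future assessments could be completed remotely (via telephone or video call) to prevent coming to the hospital".

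The first two are unconditional. The third is an invitation.

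Objective 3 in section 2.2 is to assess the impact of the tumour and "track changes in reported QoL throughout treatment and disease progression". Objective 4 asks the same for caregivers. Primary outcome 3 in section 3.8 relates the measures over time to treatment, progression and cognitive function. Primary outcome 1 judges feasibility by completion rates.

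**The concern.** Item 11 contradicts itself, and so does section 5. The end-of-study sentence in section 5 does not mention the continuation route at all. Three centres recruit, and each could follow a different sentence in good faith.

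No later analysis can recover a questionnaire that was never given. If stopping treatment tends to accompany decline, the missing forms come from the period that objectives 3 and 4 and primary outcome 3 are about. The caregiver's data would also end because of the patient's treatment status, even where the caregiver is willing to go on. Finally, the number of forms that fall due, which is the denominator of a completion rate, differs between the two rules.

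**Working it through.** This is a comparison of texts; no sample-size figure drives it. The steps are as follows.

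**1. Rules side by side.**

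| Place | Follow-up ends at |
|---|---|
| Study Summary | six months |
| Section 5, first paragraph | six months |
| Section 5, end-of-study sentence | six months, discontinuation of treatment, or death |
| Section 3.5 item 11, first sentence | six months, discontinuation of treatment, or death |
| Section 3.5 item 11, remainder | timetable continues after discontinuation, if the invitation is accepted |

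The third and fourth rows cannot both stand with the first, second and fifth.

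**2. The trigger.** Discontinuation of treatment is nowhere defined, so it is unclear whether planned completion of a course counts. The caregiver criterion in section 4.1 admits treatment expected to last three weeks or more. If completion did count, follow-up could end before the week 6 visit.

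**3. What the literal rule removes.** Section 5 schedules PGI or CaGI and the main standard questionnaires at baseline, week 2, week 6 and months 3, 4 and 6, which is six assessments. For someone stopping after week 6:
- PGI and EORTC (patient), CaGI and CarGOQoL (caregiver): months 3, 4 and 6 are lost, 3/6 = 50%.
- EQ-5D-5L (both) and MoCA (patient): scheduled at baseline, month 3 and month 6; 2/3 are lost and only baseline remains. No change from baseline in EQ-5D-5L can be formed, although section 8.3 plans to analyse changes from baseline and to compare EQ-5D-5L with the other measures.

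Section 3.5 item 10 lists only five time points, without week 2. On that list the loss is 3/5 = 60%.

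**4. Completion rate.** Take the same person, with every form completed up to week 6 and none after. If forms cease to fall due at discontinuation, completion is 3/3 = 100%. If they remain due to six months, it is 3/6 = 50%. On the five-point list the two values are 2/2 = 100% and 2/5 = 40%. The protocol does not say which denominator applies.

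**5. Precision, for scale only.** Section 8.1 gives 95% intervals for r = 0.5 of 0.28 to 0.67 (n = 60) and 0.17 to 0.73 (n = 30). Fisher's formula, tanh(atanh(0.5) ± 1.96/√(n − 3)), gives 0.282 to 0.669 and 0.170 to 0.729, so the stated figures are right. The protocol gives no discontinuation rate. Assume, purely as illustration, that 10% to 50% of the analytical sample has no month 6 data:
- Patients: n = 54 to 30; the interval runs from 0.27 to 0.68 at n = 54, and from 0.17 to 0.73 at n = 30.
- Caregivers: n = 27 to 15; the interval runs from 0.15 to 0.74 at n = 27, and from −0.02 to 0.81 at n = 15.

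These intervals show lost precision only and say nothing about bias from selective loss.

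**The case against.** The strongest reply is that continuation was intended and merely badly worded. Item 11 deals specifically with patients who come off active treatment and offers them and their caregivers the remaining timetable by telephone or video. Both groups must intend at least five clinic visits over six months to be eligible. Section 4.3 keeps participants in follow-up after a change to alternative treatment, although that is a different situation. Section 5 describes routine visits in the follow-up phase as distinct from those during chemo-radiotherapy. The study is also described as feasibility and pilot work, and the analysis plan may define the completion denominator.

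Most of this stands, and it limits the point. A reader might infer that HRQoL data stop selectively by design. The documents do not support that: it follows only where the end rule is applied literally. Nor do they support treating every short planned course as a discontinuation, since the term is undefined. The reply does not remove the conflict, however. Intention has to be inferred against two explicit sentences, and an analysis plan cannot supply forms that a site did not collect.

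**Conclusion.** The point holds as a conflict between data-collection rules resting on an undefined trigger. Where the end rule is applied, a participant stopping after week 6 loses three of six scheduled assessments and both post-baseline EQ-5D-5L assessments; a patient also loses both post-baseline MoCA assessments. That such loss is related to progression is a reasonable inference. The protocol does not say why treatment stops.

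Three stronger conclusions are tempting and should not be drawn:
- *Completion is inflated.* It would be only if forms after discontinuation were left out of the denominator, which is not stated.
- *Trajectories are biased upward.* The direction depends on the reasons for stopping, which are not given.
- *A given percentage of all forms will be lost.* That needs a discontinuation rate, its timing and the share who decline the invitation, none of which is in the protocol.

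The conflict still needs correcting, because the loss cannot be repaired afterwards and bears on two objectives and on primary outcomes 1 and 3.

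**What to change.** Reconcile the sentences as a matter of data collection only; clinical management is not affected.

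- Remove discontinuation of treatment as an end of questionnaire follow-up in section 5 and in the first sentence of section 3.5 item 11.
- State one rule: with ongoing consent, patient and caregiver assessments continue to six months, death or withdrawal, using the remote route in item 11. Withdrawal includes the existing rule in sections 3.6 and 4.3 that a patient's data collection stops on loss of capacity.
- Say whether a caregiver continues after the patient's death.
- Record the date treatment stopped. How that date enters the models can be left to the analysis plan.
- Count completion against all assessments scheduled while the participant is alive and on study.

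The cost is a wording amendment, some extra remote questionnaires by a route that already exists, and possibly a lower reported completion rate.
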